PREDIN: Pregnancy and Vitamin D Intervention study – a randomized controlled trial

Document date: 2022-01-26

NCT number: not yet assigned

INTRODUCTION

Vitamin D deficiency is common among certain risk groups in Sweden. The investigators have shown in the first large Swedish multi-ethnic population-based study, the GraviD cohort, that every tenth pregnant woman in Västra Götaland is vitamin D deficient (<30 nmol/l, 25-hydroxyvitamin D; 25OHD) (1). The prevalence of vitamin D deficiency in pregnancy was two times higher during the winter and five times higher within certain ethnic minorities. Vitamin D insufficiency was also common, as 25% had 25OHD <50 nmol/l. Thus, at northern latitudes many pregnant women are already at risk of vitamin D deficiency and insufficiency. The increasingly multi-ethnic population residing in Sweden makes vitamin D deficiency a growing clinical challenge for society and health care.

The effect of maternal vitamin D in pregnancy for maternal and offspring health needs to be clarified. In observational studies, the investigators and others show associations between poor maternal vitamin D status in pregnancy and increased odds of gestational hypertension and preeclampsia (2), fetal growth restriction (3, 4), and preterm birth (4, 5). Poor maternal vitamin D status is also linked to impaired growth in the first year of life, and potentially also to higher risk of developing obesity in childhood (6). Limited evidence suggest that maternal vitamin D supplementation improve neonatal bone mineral content (7), in neonates born during the winter at the seasonal nadir of vitamin D status. Since the evidence for positive effects of maternal vitamin D status or intake is limited, vitamin D interventions in pregnancy are warranted to clarify the causal effects of vitamin D in pregnancy and the doses required to achieve sufficient vitamin D status in deficient women.

Current recommendations for vitamin D intake in pregnancy

According to the 2012 Nordic Nutrition Recommendations, pregnant women are recommended the same dietary intake of vitamin D as the general adult population; 10 µg/day. For individuals with little or no sun exposure, 20 µg/day is recommended (8).

The national dietary survey Riksmaten from 2010 showed that median vitamin D intake was low at less than 6 µg/day in the overall adult population, and lowest among young women at 4.4-5.1 µg/day (9). The dietary intake of pregnant women is not included in this survey but results from our population based cohort study of pregnant women, show that dietary intake is around 5 µg/day also in this population and that only 6% of women reach the recommended intake through diet alone (10). As a result of the low reported intakes of vitamin D in Sweden,

the mandatory vitamin D fortification policy was extended by the National Food Agency in 2018, to include a wider range of foods and to increase the vitamin D content of fortified products (11). The effect of the new policy on vitamin D intake and status is currently unknown, but our preliminary projection data show that vitamin D intake will likely double in the pregnant population. However, those who do not consume dairy products or margarine will not benefit from the increased fortification and will remain at very low dietary vitamin D intake. Preliminary data from the investigators group show that the ethnic minority groups with high risk of vitamin D deficiency are also at high risk of a continued low vitamin D intake, as they consume less of vitamin D fortified foods. The recommendations for vitamin D intake may therefore be difficult to achieve by diet alone, despite the increased fortification, and supplement use may therefore be warranted for certain groups.

Vitamin D supplementation is recommended for risk groups of poor vitamin D status by the National Food Agency. For adults, the recommendations are to take a daily supplement of either 10 µg if dietary intake or sun exposure is low. If both dietary intake and sun exposure is low, 20 µg/day is recommended (12). There are no specific recommendations for pregnant women, so these recommendations apply also for them.

Are the recommendations sufficient?

There is an increasing body of evidence to suggest that the current recommendations are not sufficient to maintain adequate vitamin D status throughout the year. A 2020 individual participant data meta-analysis show that over 30 µg/day is needed to maintain 25OHD concentration >50 nmol/L during winter, in 90% of the adult population (13). Results also showed that very high intakes (92 µg/day) was required to ensure adequate vitamin D status among >97.5% of the population. These results suggest that the current dietary recommendation of 10 µg/day might be insufficient to maintain optimal vitamin D status for many individuals.

The current recommendations for supplemental vitamin D intake at 10 or 20 µg/day for risk groups, is likely too low to achieve the target levels of 25OHD at >50 nmol/L. One µg/day is assumed to raise 25OHD concentration by 1.2 nmol/L. Thereby, for someone with vitamin D deficiency (i.e. 25OHD <30 nmol/L), 15-40 µg/day would be needed to achieve 25OHD >50 nmol/L, depending on the severity of the deficiency.

SPECIFIC SCIENTIFIC AIMS

The double-blind randomized controlled trial (RCT) will include pregnant women with high risk of vitamin D deficiency. Women will be randomized to one of three groups: usual care, or supplementation with either 20 or 40 µg/day vitamin D/day starting in the first trimester. The PREDIN RCT will be conducted within the antenatal care units in Gothenburg with start in 2021. In addition, the investigators aim to evaluate if the overall vitamin D status and vitamin

D intake have increased since the expanded vitamin D fortification program was initiated in year 2020.

The specific aims are to test the hypotheses that:

1. Maternal vitamin D₃ supplementation with 40 µg/day will be more effective than 20 µg/d in achieving vitamin D sufficiency (25OHD ≥50 nmol/l) in pregnant women
2. Maternal vitamin D₃ supplementation (both 20 and 40 µg) during pregnancy will be more effective than usual care in obtaining vitamin D sufficiency (25OHD ≥50 nmol/l) in pregnant women
3. The expanded vitamin D food fortification program has increased the vitamin D status and vitamin D intake of pregnant women in Gothenburg since 2013-2014
4. Vitamin D status and/or vitamin D intake is related to risk of developing complications during pregnancy or delivery

METHODS AND MATERIALS

The **PREDIN RCT** is a randomized double-blind trial with three parallel arms, providing pregnant women with either usual antenatal care, or a daily pill of 20 or 40 µg/day vitamin D₃ (cholecalciferol), in the first trimester of pregnancy.

Recruitment and allocation

The study will be conducted within the antenatal care in Gothenburg. At a routine visit in early pregnancy, women will receive study information orally and in writing. A signed informed consent is needed to be included as participant in the study. According to clinical praxis, interpreters will be present when needed. In addition, study information will be translated into other languages, e.g. English, Somali and Arabic.

Inclusion criteria for screening for the RCT are age 18-45 years and gestational week <15. Exclusion criteria are multifetal pregnancy, known disorder to the metabolism of vitamin D, calcium or phosphate (e.g. adrenal gland disorders, kidney disease), ongoing treatment with vitamin D of ≥10 µg/day and difficulties understanding the study information.

Included women will be screened for risk of vitamin D deficiency, using a validated screening tool (manuscript under review), and they will be invited to complete the study questionnaires and have blood drawn for later analyses. These data will be used for aim 3 and 4.

Women at high risk of vitamin D deficiency, defined as a screening score ≥15 points, will be randomized to one of the three study arms. Blindness towards both subjects and research staff will be ensured in the two groups receiving vitamin D supplementation. For practical reasons, the group receiving usual care will be open label.

Power for sample size

Power is based on the difference in the primary outcome, proportion of vitamin D sufficiency (25OHD >50 nmol/L) at follow up in the third trimester, between the groups receiving 20 or 40 µg vitamin D per day. Assuming that 50% and 90% achieve vitamin D sufficiency in the respective groups, 17 participants per group is needed. Assuming 50% retention rate, 102 women will be included and randomized to one of the three groups using a computer generated randomization list. To reach the target sample size of 102 women, it is estimated that approximately 500 women will need to be screened. This is based on a 20% prevalence of high risk of vitamin D deficiency according to the screening tool.

Data collection

At screening, data on socio-demographic factors, ethnicity, dietary intake, eye color, sun exposure, and health status (including use of medications) will be collected using questionnaires. Blood will be drawn and banked for later analysis. Women will be followed up in the third trimester of pregnancy, through assessment of dietary intake and blood draw. Compliance and adverse events will be monitored through questions posed by the midwife in the third trimester at the follow-up visit.

Banked blood will be analyzed for 25OHD and other vitamin D metabolites, nutritional biomarkers, inflammation, hormones and gene variants related to vitamin D metabolism.

[figure not shown]

Figure 1. Study design for the PREDIN study

For all women, information on gestational complications, fetal growth and gestational age at birth will be retrieved from medical records via the antenatal care after birth. Retrieved variables for the child will include weight, length, head circumference, vitality signs (Apgar score), gestational duration, and diagnosis of small-for-gestational age, large for gestational age or intrauterine growth restriction. Data for the pregnant woman will include body weight development, hemoglobin, ferritin, plasma glucose, blood pressure delivery mode and

pregnancy complications (e.g. gestational diabetes, gestational hypertension, and preeclampsia). Analyses of genetic variants relating to D vitamin metabolism will also be analysed.

Analyses of serum 25OHD (25OHD3 and 25OHD2) and vitamin D metabolites (e.g. 3-epi-25-Hydroxyvitamin D3, 1,25-dihydroxyvitamin D [1,25(OH)2D]) and vitamin D binding proteins) in maternal blood will be performed by the golden standard method liquid chromatography tandem-mass spectrometry (LC-MS/MS) in a lab accredited by the vitamin D external quality assessment scheme (DEQAS; <http://www.deqas.org>). Analyses of serum from pregnant women will be performed in batch after the last sample collection. Other analyses of blood includes biomarkers of nutrition status (e.g. nutrients, ferritin, hemoglobin, and metabolomics), inflammation (e.g. CRP, interleukines and cytokines) and bone metabolism, hormones (e.g. cortisol, PTH and sex hormones), as well as gene variants related to vitamin D metabolism.

A total amount of 15 mL blood will be drawn at both screening and follow up. Thus, the total amount of blood drawn will be 30 mL.

Statistical analyses

Mixed models analyses will be used to investigate the change of vitamin D status over time, adjusting for potential confounders. Also, logistic regression will be performed to investigate the odds of ≥ 50 nmol/l and < 50 nmol/l at follow-up. Interactions for BMI, ethnicity and season will be investigated. First the results including all completers will be evaluated (main analysis), thereafter intention-to-treat analysis will be performed including all randomized participants, and lastly per-protocol analysis will be performed including those $> 80\%$ compliant. Differences in dropouts, compliance and missed visits will be compared between the three arms in order to detect potential bias. Logistic regression analysis will be used to assess differences in dichotomous outcomes (such as gestational complications) between treatment arms, and linear regression analysis for continuous outcome data. The study will be registered at <https://clinicaltrials.gov>.

TIME PLAN

[name] has received funding for the study including from the Swedish state under the agreement between the Swedish government and the county councils, the ALF-agreement (ALFGBG-822451 and LFGBG-932690). Ethical approvals was obtained autumn 2021 (Dnr 2021-03871). Recruitment for the PREDIN RCT will start in winter 2021 and is projected to end by winter 2024. Thereafter, analysis of blood samples will be performed, followed by data handling, statistical analyses and reporting.

REFERENCES

1. Bärebring L, et al. Vitamin D Status during Pregnancy in a Multi-Ethnic Population-Representative Swedish Cohort. *Nutrients*. 2016 Oct 22;8(10).
2. Bärebring L, et al. Preeclampsia and Blood Pressure Trajectory during Pregnancy in Relation to Vitamin D Status. *PLoS One*. 2016;11(3):e0152198.
3. Chen YH, et al. Maternal vitamin D deficiency during pregnancy elevates the risks of small for gestational age and low birth weight infants in Chinese population. *The Journal of clinical endocrinology and metabolism*. 2015 Mar 16;jc20144407.
4. Bärebring L, et al. Trajectory of vitamin D status during pregnancy in relation to neonatal birth size and fetal survival: a prospective cohort study. *BMC pregnancy and childbirth*. 2018 Feb 13;18..
5. Qin LL, et al. Does maternal Vitamin D deficiency increase the risk of preterm birth: A meta-analysis of observational studies. *Nutrients*. 2016;8(5).

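### The primary outcome is sized as a difference in proportions but analysed only on the odds scale, with no absolute effect or confidence interval prespecified

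*Combined protocol and SAP*

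**What the plan says.** Three places in the combined protocol and SAP bear on the point.

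- **Specific scientific aims.** Aim 1 is that "supplementation with 40 µg/day will be more effective than 20 µg/d in achieving vitamin D sufficiency". Aim 2 compares both doses with usual care on the same endpoint.
- **Power for sample size.** "Power is based on the difference in the primary outcome, proportion of vitamin D sufficiency", comparing the 20 and 40 µg groups in the third trimester. The group size follows from the expected rates: "Assuming that 50% and 90% achieve vitamin D sufficiency in the respective groups, 17 participants per group is needed". The total is then raised to allow for losses, to 102 women at 50% retention.
- **Statistical analyses.** For the binary endpoint, "logistic regression will be performed to investigate the odds of ≥ 50 nmol/l and < 50 nmol/l at follow-up". The other model for vitamin D status is the mixed model: "Mixed models analyses will be used to investigate the change of vitamin D status over time, adjusting for potential confounders". It describes change over time, not the share of women who reach the threshold. Other binary outcomes are treated the same way: "Logistic regression analysis will be used to assess differences in dichotomous outcomes (such as gestational complications) between treatment arms".

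No section plans a risk difference, a risk ratio, proportions standardised from the logistic model, or a confidence interval for the difference.

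**The concern.** The trial is designed around one quantity, how far apart the proportions sufficient are in two arms. The planned analysis yields another. When the outcome is common, as assumed here, the odds ratio lies far from the risk ratio and says nothing about the absolute gain unless the comparator rate is given beside it. A reader choosing between two doses would want the absolute gain and its uncertainty.

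There is also a practical problem. With about 17 completers per arm and a high success rate, an arm may contain no insufficient woman. The default logistic output then fails for the primary comparison, and the plan names no alternative.

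**Working it through.** **Inputs.** From the power section: rates 0.50 (20 µg) and 0.90 (40 µg), 17 per group, 50% retention, 102 randomised. The plan does not state alpha, sidedness, power or allocation ratio. I assume two-sided 5%, 80% power and equal allocation.

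**1. The plan's own figure.** Unpooled difference-in-proportions formula:

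n = [p1(1−p1) + p2(1−p2)] × (1.96 + 0.84)² / (p2−p1)² = (0.25 + 0.09) × 7.85 / 0.16 = 16.7, rounded up to 17.

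Then 3 × 17 = 51, and 51 / 0.5 = 102. Both stated figures reproduce, which fits sizing on the difference scale.

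**2. Effect measures at the planned rates.**

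- Odds ratio: (0.9/0.1) / (0.5/0.5) = 9.0
- Risk ratio: 0.9/0.5 = 1.8
- Difference: 0.9 − 0.5 = 40 points

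**3. What an odds ratio of 9 implies for the gain.** With comparator rate p, the other rate is 9p / (1 + 8p).

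| Comparator rate | Rate at OR 9 | Difference |
|---|---|---|
| 50% | 90.0% | 40 points |
| 70% | 95.5% | 25 points |
| 80% | 97.3% | 17 points |
| 90% | 98.8% | 9 points |

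**4. Precision at 17 per arm, planned rates (large-sample).**

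- Difference: standard error √(0.34/17) = 0.141, so 0.40 ± 0.277, or 12 to 68 points.
- Odds ratio: ln 9 = 2.197, standard error √[(4 + 11.11)/17] = 0.943, so exp(2.197 ± 1.848), or 1.4 to 57.

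**5. Chance that the odds ratio cannot be estimated.** P(all 17 sufficient at a true 90%) = 0.9^17 = 0.167. The maximum-likelihood odds ratio for 40 versus 20 µg is then infinite, with no usable Wald interval. If nobody dropped out (34 per arm), the chance would be 0.9^34 = 0.028, so the problem depends on the planned retention.

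An interval for the difference survives. Illustration with 9/17 versus 17/17, difference 0.471:

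- Wilson limits are 0.310 to 0.738 for 9/17 and 0.816 to 1 for 17/17.
- Newcombe lower limit: 0.471 − √[(1 − 0.816)² + (0.738 − 0.529)²] = 0.19.
- Newcombe upper limit: 0.471 + √[0² + (0.529 − 0.310)²] = 0.69.
- The interval is 19 to 69 points.

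**6. Power at 17 per arm, 50% versus 90%, by exact enumeration of all outcomes (two-sided 5%, no covariates).**

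| Method | Power |
|---|---|
| Wald test on log odds ratio (inestimable trials counted as not significant) | 55% |
| Newcombe interval excludes zero | 75% |
| Logistic likelihood-ratio test | 79% |
| Unpooled test of the difference | 79% |

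The loss lies in the Wald version, not in logistic regression as such.

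**The case against.** Sizing on two proportions and analysing by logistic regression is ordinary practice. Without covariates the odds ratio is 1 exactly when the difference is 0, and aims 1 and 2 are worded as hypotheses about which regimen is more effective. The plan does not name a Wald test, and the likelihood-ratio test keeps about 79% power. Nothing stops the investigators from tabulating proportions, and since the primary outcome is defined as a proportion, they may well do so. All of this stands, and it limits the point to the effect estimate and its interval. It does not supply the prespecified absolute measure that is missing.

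Two stronger readings are tempting, and the documents support neither.

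- A reader might infer that the completer, intention-to-treat and per-protocol odds ratios will not be comparable because they come from differently adjusted models. The plan does not say that the covariates differ between sets. Its phrase about confounders belongs to the mixed models, and no covariates are listed for the logistic model.
- A reader might infer that a non-significant result will be presented as equality of the two doses. No section plans or hints at an equivalence conclusion, and a wide odds-ratio interval would itself display the uncertainty.

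A further fair objection concerns remedies. Standardising a fitted logistic model with bootstrap or delta-method intervals is fragile at this size, because it meets the same separation. That is why the fix rests on an unadjusted interval.

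**Conclusion.** The point holds as a gap in the prespecified effect measure. The plan sizes its primary outcome as a 40-point difference and then commits only to an odds-scale analysis, with no absolute effect or interval. At the planned rates the odds ratio of 9 corresponds to a risk ratio of 1.8. In about 17% of trials at a true 90% rate and 17 completers, the ordinary estimate and its Wald interval would not exist.

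It would be wrong to conclude that the logistic test is invalid or that the trial must be resized on this account. The null hypothesis is the same, and the 55% power figure applies only to a Wald test, which the plan does not specify.

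The figures assume the plan's 50% and 90%, 17 completers per arm, two-sided 5% and no covariates. This should be corrected, but it does not threaten the design.

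**What to change.** In the section on statistical analyses, for aims 1 and 2:

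- Report the number and proportion of women with 25OHD ≥50 nmol/L in each arm.
- Make the between-arm difference in that proportion, with a 95% Newcombe or Miettinen-Nurminen interval, the primary effect estimate.
- Keep the logistic odds ratio as supplementary. If an arm has no insufficient women, use a likelihood-ratio test or a Firth-type penalised fit.
- Treat any covariate-standardised difference as secondary, in a named analysis set and with a fit that is robust to separation.
- State which result decides the hypothesis test, since the interval and the likelihood-ratio test can disagree in borderline data (75% against 79% power above).

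The cost is a few sentences and routine code, with no extra data. The drawback is that the primary interval is unadjusted and forgoes any precision that covariates might bring. The plan has serum analysed in batch after the last sample, so at the document date the change could be made before any 25OHD result was known.

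### At the planned 17 completers per group and 90% sufficiency, ordinary logistic regression gives no usable 40 vs 20 µg odds ratio in about 1 trial in 6; name a penalised fit and its test, and state its power

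*Combined protocol and SAP*

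**What the plan says.** The section on power ties the calculation to sufficiency in the third trimester, 40 vs 20 µg: "Power is based on the difference in the primary outcome, proportion of vitamin D sufficiency". It continues: "Assuming that 50% and 90% achieve vitamin D sufficiency in the respective groups, 17 participants per group is needed". Allowing for loss to follow-up, it adds: "Assuming 50% retention rate, 102 women will be included and randomized". It gives no alpha, sidedness, target power, test or formula.

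Under Statistical analyses, the binary outcome is handled as follows: "logistic regression will be performed to investigate the odds of" being at or above 50 nmol/l, or below it, at follow-up. On the analysis set: "First the results including all completers will be evaluated (main analysis"), with intention-to-treat and per-protocol analyses after it. On effect modification: "Interactions for BMI, ethnicity and season will be investigated". That sentence follows both the mixed models and the logistic regression and is not tied to either.

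No penalised or exact method is named, and nothing is said about an arm with no insufficient women. The Data collection section says of the assays: "Analyses of serum from pregnant women will be performed in batch after the last sample collection".

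**The concern.** The main analysis is in completers, and retention is planned at 50%, so 17 per arm is the size at which the logistic model is expected to be fitted. With 90% of 17 women sufficient, the expected number of insufficient women in the 40 µg arm is only 1.7, and zero is not a rare result. When it is zero, the maximum-likelihood odds ratio is infinite, and the Wald standard error and p-value are artefacts of where the optimiser stopped.

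This happens when the 40 µg arm does as well as it can, which is close to the best result for aim 1. The analyst would notice, but would then choose a substitute after seeing the data, and the substitutes differ in type I error and power. Because the power section names no test, a reader cannot tell what power the planned analysis has.

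**Working it through.** **Inputs.** From the power section: 50% (20 µg), 90% (40 µg), 17 completers per group, 50% retention, 102 randomised. Assumed because the protocol does not state them: two-sided 5%, 80% target power, equal allocation (102 = 3 × 34), and ordinary maximum likelihood for the logistic regression.

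**1. The protocol's own figure.** Normal formula with unpooled variance: (1.960 + 0.842)² × (0.5×0.5 + 0.9×0.1) / 0.4² = 16.68, rounded up to 17. Then 17/0.5 = 34 per arm and 3 × 34 = 102. The figure reproduces. At the same two-sided 5% and 80%, the arcsine formula gives 19, the pooled-variance formula 20 and the continuity-corrected formula 25. A one-sided 5% pooled formula gives 16, so the intended sidedness cannot be recovered from the number.

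**2. Chance of an all-sufficient 40 µg arm.** This is p^n:

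| True rate | 17 completers | 25 completers | 34 completers |
|---|---|---|---|
| 85% | 6.3% | 1.7% | 0.4% |
| 90% | 16.7% | 7.2% | 2.8% |
| 95% | 41.8% | 27.7% | 17.5% |

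At the planning values this is 0.9^17 = 0.1668, or 1 in 6.0. The 20 µg arm at 50% adds about 0.00002. In that case the odds ratio for 40 µg vs usual care is not finite either: it is infinite if usual care has any insufficient woman and undefined if it has none.

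**3. Example, 9/17 vs 17/17.** An ordinary fit returned a log odds ratio of 22.4 with standard error 11,689 and Wald p = 0.998. Firth's fit gives an odds ratio of 31.3 (profile 95% CI 3.3 to 4,217) and penalised likelihood-ratio p = 0.0009. Fisher's exact test gives p = 0.0027. The difference in proportions is 8/17 = 47.1 points (Newcombe 95% CI 19.2 to 69.0).

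**4. Example near the expected result, 9/17 vs 15/17.** The ordinary odds ratio is (15/2)/(9/8) = 6.7. Firth gives (15.5/2.5)/(9.5/8.5) = 5.5 (1.2 to 34.5), p = 0.027. The difference is 6/17 = 35.3 points (4.5 to 58.9).

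**5. Power and type I error.** All 18 × 18 outcomes were enumerated at 17 per arm, unadjusted, two-sided 5%. With two arms, Firth's fit equals adding 0.5 to each cell.

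| Test | Power, 50% vs 90% | Maximum type I error, common rates 1–99% |
|---|---|---|
| Ordinary Wald, non-finite fits counted as not significant | 55.5% | 5.8% |
| Wald, likelihood ratio for empty cells | 72.1% | 8.0% |
| Ordinary likelihood ratio | 79.2% | 8.4% |
| Firth, penalised likelihood ratio | 75.0% | 5.8% |
| Pearson chi-square, uncorrected | 75.0% | 5.8% |
| Fisher exact | 62.6% | 2.4% |

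The 8.4% and 8.0% occur near common rates of about 10% or 90%. At a common rate of 70% the corresponding errors are 6.1% and 4.1%. A Wald test on the Firth fit has 65.4% power, so the test must be named as well as the fit. With one-sided 5%, the Firth likelihood-ratio test has 85.0% power. With all 34 per arm observed, its two-sided power is 97%.

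**6. Interactions (illustration only).** Suppose season has two levels, splits the 40 µg arm 8/9, is fitted in the logistic model, and sufficiency is 90% in each cell. The chance of at least one all-sufficient cell is then 1 − (1 − 0.9^8)(1 − 0.9^9) = 65%. With a 4/13 split it is 74%.

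**The case against.** A reader might infer from the p = 0.998 that the trial would miss its aim 1 result in 1 case in 6. The documents do not support that. Given 17/17 in the 40 µg arm and a true 50% in the 20 µg arm, Fisher's test is significant in 97.5% of cases, Firth's in 99.4% and the ordinary likelihood-ratio test in 99.9%. These three disagree only when the 20 µg arm has 13 or 14 of 17 sufficient. No competent analyst would report the Wald output as it stands. This part of the objection stands: what is lost is the estimate, its interval and a test chosen beforehand, rather than the conclusion.

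A second objection is that Firth's method is one choice among several. For the unadjusted two-arm comparison this is true, since the uncorrected Pearson chi-square rejects exactly the same tables. What Firth adds is a finite odds ratio and a way to include covariates, within the logistic framework the protocol already uses.

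Third, the 1 in 6 depends on 50% retention and a rate of exactly 90%, and it falls quickly with more completers. That is so, but these are the protocol's own planning values, and the analysis should work at them.

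Fourth, one might infer that the season interaction will usually fail. The protocol gives neither the number of seasons nor the split, and does not say that interactions belong to the logistic model. In a mixed model of continuous 25OHD this problem does not arise.

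Finally, one might read 75% as proof that 17 was miscalculated. It was not. The gap lies between an unstated normal approximation and the test that would be used.

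**Conclusion.** The concern holds in a limited form and should be fixed. At the protocol's own values, the planned logistic regression has a 16.7% chance of giving no usable odds ratio, Wald interval or Wald test for the powered comparison, and the plan has no rule for this. The 16.7% needs no assumed alpha. The power and error figures assume two-sided 5%, 17 completers per arm and no covariates. Adding covariates or interactions to the logistic model cannot make the problem rarer. A fallback chosen after seeing the data could carry a type I error of up to about 8%, against at most 5.8% for the named test. The omission of alpha, sidedness, target power and test is a separate, plain gap in the power section. Neither point shows that 102 is wrong.

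**What to change.** **Statistical analyses.** Replace the logistic sentence with wording such as: *Sufficiency at follow-up will be compared between 40 and 20 µg by logistic regression with Firth's penalised likelihood, using a two-sided 5% penalised likelihood-ratio test. The odds ratio will be reported with its profile penalised-likelihood 95% CI, and the difference in proportions with a Newcombe 95% CI. The same fit will be used against usual care and for any interactions fitted in the logistic model.*

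**Power for sample size.** State the alpha, sidedness, target power and formula that produced 17. Add that 17 completers per group give about 75% power for 50% vs 90% with the named test, unadjusted, at two-sided 5%. If a one-sided 5% test was intended (aim 1 is directional), say so and give 85%. No change to the 102 is asked for. The sponsor may wish to note that this test first exceeds 80% at 19 completers per group (81.2%).

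**Cost.** A few sentences, with no extra women, visits or samples. Because 25OHD is assayed in one batch at the end, the method can be fixed before any outcome is known. There are two downsides. Firth's method pulls odds ratios towards 1 (5.5 instead of 6.7 for 9/17 vs 15/17). When an arm is all sufficient, the upper limit of the odds ratio is very wide, which is why the difference in proportions should be reported with it.

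### The per-protocol analysis needs compliance above 80%, but the plan has only midwife questions at one late visit and no rule that turns the answers into a percentage

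*Combined protocol and SAP*

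**What the plan says.** The Statistical analyses section names three analysis sets in order. Completers come first and are the main analysis, and all randomized women come second. The third is described thus: "lastly per-protocol analysis will be performed including those" who are more than 80% compliant. The same section plans a further use of the adherence data: "Differences in dropouts, compliance and missed visits will be compared between the three arms in order to detect potential bias".

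The measurement is described once, under Data collection: "Compliance and adverse events will be monitored through questions posed by the midwife in the third trimester at the follow-up visit". The wording of the questions is not given. No pill count, return of packs, diary or contact between enrolment and that visit is described, and no formula for the percentage.

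Under Methods and materials the regimen is "a daily pill of 20 or 40 µg/day vitamin D₃ (cholecalciferol), in the first trimester of pregnancy"; the aims section says that supplementation starts in the first trimester. Entry is before gestational week 15. The 20 and 40 µg arms are blinded to women and staff. Usual care is open label, and no study pill is described for it.

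**The concern.** A numerical threshold needs an instrument that yields the number. Here a woman is asked in the third trimester about a daily pill begun in early pregnancy, and someone must then decide whether she took more or less than 80% of them. The plan does not say how.

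The two possible errors have different costs. Wrongly leaving out an adherent woman mainly costs numbers. Wrongly admitting a woman with low intake also pulls the two dose arms together, because the 25OHD difference between them depends on the pills being taken. The 20 versus 40 µg comparison is the subject of aim 1, and the per-protocol analysis is the one meant to show it among women who took their pills. The planned comparison of compliance between the two supplement arms rests on the same answers.

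**Working it through.** **1. The plan's own figure.** Power for sample size gives 50% versus 90% sufficient, 17 per group and 102 in total at 50% retention. Alpha and power are not stated; I assume two-sided 0.05 and 80%. The unpooled formula gives

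n = (1.960 + 0.842)² × (0.5×0.5 + 0.9×0.1) / 0.4² = 7.849 × 0.34 / 0.16 = 16.68, rounded up to 17.

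Then 17 / 0.5 = 34 per arm, and 3 × 34 = 102. The figure reproduces, and the adherence question does not change it.

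**2. Length of recall.** The documents give only entry before week 15 and a third-trimester visit. Assume a start at weeks 8–14 and a visit at weeks 28–38.
- Shortest: 28 − 14 = 14 weeks = 98 pills; 20% missed is about 20 pills.
- Longest: 38 − 8 = 30 weeks = 210 pills; 20% missed is 42 pills.

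**3. What intake does to the dose contrast.** From the section Are the recommendations sufficient?: "One µg/day is assumed to raise 25OHD concentration by 1.2 nmol/L". Full intake adds 1.2 × 20 = 24 and 1.2 × 40 = 48 nmol/L, a gap of 24. If intake is equally reduced in both arms, the gap is 24 × intake: 19.2 at 80%, 12 at 50% (12 versus 24 nmol/L), and 0 at none.

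To turn this into proportions, take follow-up 25OHD as normal and let the plan's 50% and 90% apply at full intake. The mean in the 20 µg arm is then 50, the mean without supplement is 50 − 24 = 26, and the SD is 24 / 1.2816 = 18.7 nmol/L.

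| True intake, both arms | 20 µg | 40 µg | Difference (points) |
|---|---|---|---|
| 100% | 50% | 90% | 40 |
| 80% | 40% | 78% | 38 |
| 50% | 26% | 50% | 24 |
| 0% | 10% | 10% | 0 |

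Errors close to the 80% line therefore matter little. Low intake passed off as high is what matters.

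**4. Wrongly admitted women.** Suppose a share m of the per-protocol set has low true intake and the rest full intake. For m = 20% at half intake:
- 20 µg: 0.8 × 50.0 + 0.2 × 26.1 = 45.2%
- 40 µg: 0.8 × 90.0 + 0.2 × 50.0 = 82.0%
- difference: 36.8 points

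Power uses the unpooled formula with 17 per arm.

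| m | Their true intake | 20 µg | 40 µg | Difference (points) | Power |
|---|---|---|---|---|---|
| 0 | – | 50% | 90% | 40 | 81% |
| 10% | half | 48% | 86% | 38 | 74% |
| 20% | half | 45% | 82% | 37 | 67% |
| 20% | quarter | 43% | 77% | 34 | 57% |
| 20% | none | 42% | 74% | 32 | 51% |
| 40% | none | 34% | 58% | 24 | 30% |

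The values of m are assumptions; the documents give none. Seventeen is the planned number of completers, so a real per-protocol set may be smaller and the power column is only indicative.

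**5. Cost of excluding them correctly.** Removing 20% of 17 leaves about 14 per arm. At 50% versus 90%, power is then 73%, against 67% if women at half intake stay in and 51% if women with no intake stay in. The difference returns to 40 points.

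**The case against.** The strongest reply is that little depends on this. Per-protocol comes last of three analyses, and the trial's sizing and main result do not use the cut-off. That stands. A reader might infer that the measure blurs the aim 1 comparison itself, but the completer and intention-to-treat results would be the same whatever instrument is used. If women do not take their pills, those analyses are diluted by the non-adherence itself, which a pill count would not alter.

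A reader might also infer that partial adherence erases the contrast, since half intake at 40 µg equals full intake at 20 µg (both +24 nmol/L). That pairs poor adherence in one arm with perfect adherence in the other. The two arms are blinded, and nothing in the documents suggests that adherence or over-reporting differs by dose. With equal intake the gap shrinks, and the expected effect is attenuation rather than bias towards one dose.

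Three more points stand. The questions are not reproduced, so that they rely on recall of the whole period is inferred from there being one follow-up visit. The documents do not say that answers run high, or that the midwife is the woman's own. And the compliance comparison is planned to detect bias; the plan does not offer it as a way to tell poor adherence from a lack of dose effect, so it should not be faulted on that ground.

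Finally, a pill count has faults of its own: lost or discarded pills count as taken, and mixing counts with answers puts two instruments into one small set. The fix has to deal with both. It does not follow that the matter is only one of wording. The plan names a percentage with no source for it, and a count not made at the visit is hard to recover later.

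**Conclusion.** The point holds for the per-protocol analysis and for the compliance comparison between the two supplement arms, and goes no further. The plan sets a cut-off above 80% without an instrument or rule that gives the percentage. Women with low intake may be admitted, which would dilute the per-protocol 20 versus 40 µg difference.

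Over 10–40% wrongly admitted and true intake between none and half, the modelled difference falls from 40 to between 38 and 24 points. These figures rest on the plan's 1.2 nmol/L per µg/day, a normal model calibrated to its 50% and 90%, equal misclassification in both arms, and assumed misclassification rates. The true size is unknown. This is a minor point, worth acting on because the remedy is cheap and must be in place before follow-up visits.

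**What to change.** In Data collection: record the number of pills issued to each woman, ask her to bring the container to the planned third-trimester visit, and count the remainder. Keep the midwife's questions alongside the count to identify lost or discarded pills.

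In Statistical analyses:
- Define compliance as (pills issued − pills returned) / days from start to visit.
- Use the midwife's questions as a fallback only when no container is returned, and flag those women.
- Report the per-protocol result with and without the fallback cases.
- State that the rule above 80% applies only to the two supplement arms, since no study pill is described for usual care.

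The cost is a few minutes at an existing visit and one reminder, which may need translation or an interpreter; no extra visit or sample is needed. Some containers will be forgotten, and the per-protocol set may be smaller. The document is dated January 2022 and gives winter 2021 as the start of recruitment, so some pills may already have been issued uncounted; those women would be fallback cases.
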